Brentuximab vedotin was studied as monotherapy in 160 patients in two pivotal phase 2 studies (SG035-0003 and SG035-0004) (see section 5.1 of SmPC). Serious infections and opportunistic infections have been reported in patients treated with this medicine (see section 4.4 of SmPC). In the phase 2 population, 16% of patients experienced treatment-related infections. Serious adverse drug reactions were: neutropenia, thrombocytopenia, constipation, diarrhea, vomiting, pyrexia, peripheral motor neuropathy and peripheral sensory neuropathy, hyperglycemia, demyelinating polyneuropathy, tumor lysis syndrome and Stevens-Johnson syndrome.

The most frequently observed adverse reactions in patients receiving this treatment were: peripheral sensory neuropathy, fatigue, nausea, diarrhea, neutropenia, vomiting, pyrexia, and upper respiratory tract infection. Overall, 20% of HL patients and 28% of systemic ALCL patients in the pivotal studies (Studies SG035-0003 and SG035-0004) discontinued treatment

because of AEs. AEs that led to the treatment discontinuation of ≥ 2 HL or sALCL patients were peripheral sensory neuropathy and peripheral motor neuropathy.

The safety data reported from the phase 1 dose escalation and clinical pharmacology studies (n=15 patients) and from the Named Patient Program (NPP; n= 26 patients), in patients with relapsed or refractory HL who had not received an autologous stem cell transplant (see section 5.1 of SmPC), and were treated with the recommended dose of 1.8 mg/kg every three weeks, were consistent with the safety profile of the pivotal clinical studies.

Description of selected adverse reactions

Doses were reduced in patients for peripheral sensory neuropathy, which was the only AE that led to the dose reduction of more than 1 patient in either of the phase 2 studies. Adverse events that led to dose delays in the most patients were neutropenia, peripheral sensory neuropathy, and thrombocytopenia; the total percentage of doses delayed in HL patients was 8% (80 of 985 doses) and the total percentage of doses delayed in sALCL patients was 10% (47 of 476 doses). A total of 13 patients had an interruption or early stoppage to the infusion due to an AE.

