Thirty-four patients (21%) in SG035-0003 and SG035-0004 had a treatment-emergent AE of neutropenia; for 20% of patients, neutropenia was \geq Grade 3 (13% at Grade 3 and 7% at Grade 4). The first onset of neutropenia (any grade) occurred within the first 4 cycles of treatment for most patients (82%), suggesting that neutropenia is not cumulative. Neutropenia \geq Grade 3 tended to develop after a median of 2 doses and last a median of approximately 1 week. Of the 7% of patients with Grade 4 neutropenia, 3 had neutropenia that lasted ≥ 7 days. No treatment-emergent AEs of febrile neutropenia were reported in the pivotal studies and no patient discontinued treatment because of neutropenia. In the pivotal studies (Studies SG035-0003 and SG035-0004), 89 patients (56%) had at least 1 treatment-emergent AE within the PN SMQ (56 patients [55%] in SG035-0003 and 33 patients [57%] in SG035-0004). The peripheral neuropathy symptoms that occurred in $\geq 5\%$ of HL or ALCL patients were peripheral sensory neuropathy (47% HL, 41% ALCL), peripheral motor neuropathy (12% HL, 5% ALCL), paraesthesia (9% ALCL), and neuralgia (5% ALCL).

The median time to onset of any grade PN SMQ event was approximately 12.4 (HL) to 15.0 (ALCL) weeks. Peripheral neuropathy tended to worsen with longer treatment exposure. Median time to onset of Grade 2 neuropathy was 27.3 weeks for HL patients and 17.0 weeks for ALCL patients. Median time to onset of Grade 3 neuropathy was 38.0 weeks for HL patients and 36.1 weeks for ALCL patients.

PML has been reported in patients treated with brentuximab vedotin and has been fatal in

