1.6 Potential Risks of brentuximab vedotin

As detailed in the Clinical Experience Section 1.4, brentuximab vedotin monotherapy has demonstrated therapeutic activity in CD30+ hematological malignancies.

Brentuximab vedotin treatment causes a peripheral neuropathy that is predominantly sensory. Cases of peripheral motor neuropathy have also been reported. Monitoring patients for symptoms of neuropathy, such as hypoesthesia, hyperesthesia, paresthesia, discomfort, a burning sensation, neuropathic pain or weakness is required. Patients experiencing new or worsening peripheral neuropathy may require brentuximab vedotin dose modifications, including a dose delay (see Section 5.2 Dose Modification Guidelines).

Infusion-related reactions, including anaphylaxis, have occurred with brentuximab vedotin.¹⁷ Monitoring of patients during infusion is required. If anaphylaxis occurs, the administration of brentuximab vedotin should be immediately and permanently discontinued and appropriate medical therapy administered. If an infusion-related reaction occurs, the infusion should be interrupted and appropriate medical management instituted. Patients who have experienced a prior infusion-related reaction should be premedicated according to institutional guidelines for subsequent infusions. Premedication may include acetaminophen, an antihistamine and a corticosteroid.

Clinically significant laboratory abnormalities were to be reported as adverse events per the phase 2 study protocols. The clinical laboratory parameters for which the most patients had new or worsening shifts to \geq Grade 3 were low neutrophils (11%), lymphocytes (11%), platelets (6%), leukocytes (5%), and high glucose (6%). Only 1 patient in the phase 2 studies had Grade 3 ALT and AST.

Any treatment that can decrease immune function may contribute to malignancy and infections; patients are to be monitored for these events during the treatment period and up to and including 30 days after the last dose of frontline therapy.

Complete blood counts should be monitored prior to each dose of brentuximab vedotin and more frequent monitoring should be considered for patients with Grade 3 or 4 neutropenia. Prolonged (\geq 1 week) severe neutropenia can occur. If Grade 3 or 4 neutropenia develops, manage by dose delays, reductions, or discontinuations (see Section 5.2 Dose Modification Guidelines).

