6.2 Dose Modification Guidelines

Brentuximab vedotin dose modifications may change depending on the disease and combination with other drug(s).

Table 6-1 and Table 6-2 detail the recommended brentuximab vedotin dose modifications to be enacted in the event of treatment-associated toxicity.

Table 6-1 Recommended brentuximab vedotin Dose Modifications for Treatment-Associated Toxicity Excluding Neuropathy

Toxicity	≤Grade 2	Grade 3	Grade 4
Non-hematologic (excluding neuropathy)	Continue at same dose level.	Withhold dose until toxicity is ≤ Grade 1 or baseline, then resume treatment at the same dose and schedule ^a .	Withhold dose until toxicity is ≤ Grade 1 or has returned to baseline, then reduce dose to 1.2 mg/kg and resume treatment, or discontinue at the discretion of the investigator. ^a
Hematologic	Continue at same dose level.	Withhold dose until toxicity is ≤ Grade 2, or baseline, then resume treatment at the same dose level ^b . Consider growth factor support (G-CSF or GM-CSF) in subsequent cycles. ^b	Withhold dose until toxicity is ≤ Grade 2 or baseline, then resume treatment at the same dose and schedule. Consider growth factor support (G-CSF or GM-CSF) in subsequent cycles for patients who develop Grade 3 or Grade 4 neutropenia. ^b

NOTE: Grading based on National Cancer Institute (NCI) Common Terminology Criteria for Adverse Events (CTCAE) v. 4.03

- a Patients who develop Grade 3 or 4 electrolyte laboratory abnormalities may continue study treatment without interruption. Brentuximab vedotin will be held for clinically meaningful Grade 3 or 4 electrolyte abnormalities.
- b Patients who develop Grade 3 or 4 lymphopenia may continue study treatment without interruption.

Table 6-2 Dosing Recommendations for Treatment-Emergent or Worsening Peripheral Sensory or Motor Neuropathy

Severity of Peripheral Sensory or Motor Neuropathy (Signs and Symptoms [abbreviated description of CTCAE])	Modification of Dose and Schedule
Grade 1 (Asymptomatic; clinical or diagnostic observations only; intervention not indicated; paresthesia and/or loss of deep tendon reflexes)	Continue with the same dose and schedule
Grade 2 (Moderate symptoms; limiting instrumental activities of daily living)	Withhold dose until toxicity returns to \leq Grade 1 or baseline, then restart treatment at a reduced dose of 1.2 mg/kg every 3 weeks
Grade 3 (Severe symptoms; limiting self care activities of daily living)	

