6.6 Management of Clinical Events

Peripheral Neuropathy

Collectively, the data support that peripheral neuropathy is an effect of cumulative exposure to brentuximab vedotin. The first onset of any grade peripheral neuropathy increased incrementally with increasing numbers of cycles, and a trend toward increased incidence of first onset of Grade 3 peripheral neuropathy and peripheral motor neuropathy in later cycles was apparent. In line with these observations, the incidences of peripheral neuropathy (any SMQ event, Grade 3 event, and/or motor event) were highest in later cycles.

Neuropathy associated with brentuximab vedotin was managed using a combination of dose delay and reduction to 1.2 mg/kg. Dose delay and reduction appeared to mitigate worsening of neuropathy. For new or worsening Grade 2 or 3 neuropathy, dosing should be held until neuropathy improves to Grade 1 or baseline and then restarted at the 1.2 mg/kg dose level (or as specified in individual protocols). For Grade 4 peripheral neuropathy, brentuximab vedotin should be discontinued.

Hematological Toxicities

The hematological AEs of thrombocytopenia, anemia, and neutropenia were reported in the pivotal studies. Neutropenia was the most common hematological AE (21%) and was not unexpected based on the toxicology results from the sponsor's nonclinical program and phase 1 safety and clinical pharmacology studies. Although neutropenia was a common treatment-emergent AE in the pivotal studies, it appeared to be well managed with the protocol-specified recommendations for hematologic toxicity (i.e., dose delay, growth factor support). The median duration of Grade 3 or Grade 4 neutropenia was limited (1 week); 3 patients had Grade 4 neutropenia that lasted ≥ 7 days. Less than half of the patients with Grade 3 or 4 neutropenia had temporally associated infections, and the majority of temporally associated infections were Grade 1 or 2. Although not reported in the pivotal studies, febrile neutropenia has been reported in additional completed studies with brentuximab vedotin. Patients should be monitored for cytopenias.

For new or worsening Grade 3 or 4 neutropenia, dosing should be held until neutropenia improves to \leq Grade 2 or baseline and then restarted at the same dose level (or as specified in individual protocols). Growth factor support (G-CSF or GM-CSF) should be considered for subsequent cycles (refer to Dose Modification Section 6.2).

Infusion-Related Reactions

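### Section 1.6 names reduction and discontinuation for Grade 3-4 neutropenia, but Table 6-1 and Section 6.6 give neither, so Grade 4 neutropenia recurring despite growth factor is by default redosed at the same dose

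*Combined protocol and SAP*

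**What the plan says.** Three parts of the protocol deal with severe neutropenia.

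- **Section 1.6** names three actions: "If Grade 3 or 4 neutropenia develops, manage by dose delays, reductions, or discontinuations". It then refers to the Dose Modification Guidelines as Section 5.2. Section 5.2 is the exclusion criteria; the guidelines are Section 6.2.
- **Section 6.2, Table 6-1**, presented as the modifications to enact when toxicity occurs, gives for Grade 4 hematologic toxicity: "Withhold dose until toxicity is ≤ Grade 2 or baseline, then resume treatment at the same dose and schedule". Growth factor is to be considered in later cycles. The Grade 3 hematologic cell has the same content. The Grade 4 non-hematologic cell goes further once toxicity has resolved: "then reduce dose to 1.2 mg/kg and resume treatment, or discontinue at the discretion of the investigator".
- **Section 6.6** repeats the hematologic rule. Dosing is held until neutropenia is back to "Grade 2 or baseline and then restarted at the same dose level (or as specified in individual protocols"). This is the individual protocol, and it specifies nothing more for neutropenia.

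Section 6.12 lets the investigator withdraw a patient for an adverse event, whatever the toxicity.

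**The concern.** Two of the three actions named in Section 1.6 have no counterpart in the section it points to. This hardly matters for a first episode, where hold-and-resume with growth factor considered is reasonable. It matters for a patient in whom those measures have already been tried and Grade 4 neutropenia has come back. An investigator who follows the table gives that patient the same dose again. One who follows Section 1.6 may reduce or stop, but finds no dose level or trigger for doing so. Sites could therefore handle the same event differently.

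The risk is infection during severe neutropenia. Section 6.6 notes that "febrile neutropenia has been reported in additional completed studies with brentuximab vedotin", although none was reported in the two pivotal studies. Section 6.3 also sends patients who become neutropenic on strong CYP3A4/P-gp inhibitors to Table 6-1, so that row is where an investigator will look.

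**Working it through.** **Text comparison**

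| Action for neutropenia | Section 1.6 (Grade 3-4) | Table 6-1, hematologic, Grade 3 | Table 6-1, hematologic, Grade 4 | Section 6.6 (Grade 3-4) |
|---|---|---|---|---|
| Delay or hold | Yes | Yes | Yes | Yes |
| Growth factor | Not in this sentence | Consider | Consider | Consider |
| Reduce | Yes, no level given | No | No | No |
| Discontinue | Yes, no trigger given | No | No | No |
| Step for recurrence | No | No | No | No |

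The only reduced dose in the protocol is 1.2 mg/kg. It is used for Grade 4 non-hematologic toxicity (Table 6-1) and for Grade 2-3 neuropathy (Table 6-2). It is not offered for neutropenia in either table or in Section 6.6.

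**Cross-references in Section 1.6.** It cites 5.2 twice, 5.5 once and 5.6 once. By section title these should be 6.2, 6.5 and 6.6. Section 5 ends at 5.2.

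**How many patients.** Inputs: planned N = 25 (Section 4.2); 160 patients in the two pivotal studies, Grade 4 neutropenia in 7%, and 3 patients with Grade 4 neutropenia lasting at least 7 days (Section 1.4). Applying these rates here is an assumption, because the pivotal patients had Hodgkin lymphoma or systemic ALCL. Intervals are exact two-sided 95% limits.

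1. Any Grade 4 neutropenia: 0.07 × 25 = 1.75, about 1.8 patients. Chance of at least one: 1 − 0.93^25 = 0.84. Since 0.07 × 160 = 11.2, take 11/160; its interval is 3.5% to 12.0%, or 0.9 to 3.0 of 25.
2. Grade 4 lasting at least 7 days: 3/160 = 1.9%; × 25 = 0.5 patients. Interval 0.4% to 5.4%, or 0.1 to 1.3 of 25.
3. Past dose reductions for neutropenia: Section 1.4 says of peripheral sensory neuropathy that it was the adverse event "which was the only AE that led to the dose reduction of more than 1 patient in either of the phase 2 studies". Neutropenia therefore led to reduction in at most one patient per study, so at most 2/160 = 1.25%; × 25 = 0.3 patients. Upper limit for 2/160 is 4.4%, or 1.1 of 25.
4. Past discontinuations: "no patient discontinued treatment because of neutropenia", so 0/160. Upper limit 2.3%, or 0.6 of 25.
5. Size of the reduction: 1.2/1.8 = 0.667, a one-third lower dose.

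The documents give no rate of Grade 4 recurrence despite growth factor, so the group that would use the new step cannot be sized directly. It is a subset of item 1. Items 3 and 4 show how seldom such steps were used before, under whatever rules those studies had.

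**The case against.** The strongest reply is that the protocol already permits what is asked. Section 1.6 is part of the protocol and names reduction and discontinuation; the only reduced dose is 1.2 mg/kg; Table 6-1 is titled as recommended, and Section 6.2 opens by allowing that modifications may vary. Read together, the table is the default and Section 1.6 allows more. This stands in part. A reader might infer that no written option to reduce exists, or that 1.8 mg/kg is compulsory. The documents do not support either reading: Section 1.6 is such an option, and a patient already reduced for another toxicity would resume at 1.2 mg/kg. What remains is that the permission sits in a background section, gives no level or trigger, and defers to a table that does not contain it.

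A reader might also infer that the patient must be either redosed or removed from the study. That does not follow. Section 4.1 lets patients stop therapy at any time, the heading of Section 6.12 separates ending treatment from ending participation, and footnote a to the Schedule of Events follows all treated patients for PFS and OS.

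The experience is also reassuring. Section 6.6 says of neutropenia in the pivotal studies that "it appeared to be well managed with the protocol-specified recommendations for hematologic toxicity", meaning delay and growth factor. Those studies reported no febrile neutropenia, and the one fatal case described in Section 1.4 followed a single 3.6 mg/kg dose, twice the dose used here. Counts are checked before every dose, and no dose is given until recovery to Grade 2 or baseline. This supports same-dose resumption after a first event and keeps the point small. It does not tell the investigator what to do once delay and growth factor have failed.

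**Conclusion.** The conflict is real and can be confirmed by reading Section 1.6 against Table 6-1 and Section 6.6. By default, the operative table redoses Grade 4 neutropenia recurring despite growth factor at the same dose, with no reduction or discontinuation step of its own. Section 1.6 names both actions and Section 6.12 allows termination for an adverse event, so this is an unclear rule with a poor default. It does not bar an investigator from acting.

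The effect is small: about 1.8 of 25 patients with any Grade 4 neutropenia (0.9 to 3.0), of whom an unknown fraction would recur despite growth factor. These figures assume that the pivotal rates carry over to this population. It would be tempting to assume a recurrence rate and quote a chance that the step is needed, but nothing in the documents supports a value. Sample size, error rates and analysis are unaffected. The change is worth making because it is cheap and removes an ambiguity in a dosing-safety rule.

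**What to change.** 1. Keep hold-and-resume at the same dose, with growth factor considered, for a first event.
2. Add to the Grade 4 hematologic cell of Table 6-1: *Grade 4 neutropenia recurring despite growth factor support: reduce to 1.2 mg/kg or discontinue at the discretion of the investigator.* This is the option that the Grade 4 non-hematologic cell already has.
3. Add the same sentence to Section 6.6.
4. In Section 1.6, keep the existing wording on neutropenia and correct only the cross-references: 5.2 (twice), 5.5 and 5.6 become 6.2, 6.5 and 6.6. Replacing that wording with a bare pointer to Table 6-1 would remove the broader permission for cases that the new step does not cover, such as recurrent Grade 3 neutropenia or a very prolonged first Grade 4 episode.

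The cost is one table cell, one sentence and four cross-references. Visits, sample size and analysis do not change. The clinical downside is a one-third lower dose in about one patient or fewer, judged from the pivotal reduction experience (0.3 of 25 expected at most 2/160, upper limit 1.1).

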2 STUDY OBJECTIVES

2.1 Primary Objectives

To evaluate the overall response rate (ORR) of brentuximab vedotin in relapsed or refractory EBV- and CD30-positive lymphomas

2.2 Secondary Objectives

The key secondary objective is

To evaluate the safety profile of brentuximab vedotin using CTCAE version 4.03

Other secondary objectives include:

- To calculate progression-free survival (PFS) time
- To calculate the duration of response
- To calculate overall survival (OS) time

2.3 Exploratory Objectives

The exploratory objectives include:

- To determine the CD30-positive rate of EBV-positive lymphomas
- To compare ORR according to the CD30 expression level
- To compare ORR according to the soluble CD30 level
- To compare ORR according to the EBV copy number

3 STUDY ENDPOINTS

3.1 Primary Endpoints

The primary endpoint is

ORR using the revised response criteria for malignant lymphoma or modified SWAT criteria

3.2 Secondary Endpoints

The key secondary endpoint is

AEs, SAEs, and assessments of clinical laboratory values

Other secondary endpoints include:

- PFS
- Duration of response
- CR rate
- The rate of interim PET-negativity
- OS

3.3 Exploratory Endpoints

Exploratory endpoints include:

- CD30-positivity
- Qualitative and semi-quantitative measures of CD30 expression
- Serum concentrations of soluble CD30 receptor
- Serum concentrations of EBV titer

4 STUDY DESIGN

4.1 Overview of Study Design

This is an open-label, non-randomized, multi-center, phase II trial of brentuximab vedotin to evaluate ORR primarily in patients with EBV- and CD30-positive lymphomas. The ORR will be evaluated based on the revised Cheson's criteria¹ or modified SWAT criteria² in case of cutaneous EBV- and CD30-positive lymphomas. Patients may receive up to 16 cycles of brentuximab vedotin.

Tumor measurements will be assessed (CT and PET scans) at screening, after completion of cycle 2 (Cycle 2 Day 21 ± 7 day), and at 4 to 8 weeks after the last dose of brentuximab vedotin. CT scans only will be used for the disease assessment follow-up every 3 months until the study closure.

Safety will be evaluated according to National Cancer Institute Common Terminology Criteria for Adverse Events (NCI CTCAE), Version 4.03, as well as by measuring changes from baseline in the patient's vital signs, ECOG performance status, electrocardiogram (ECG), and clinical laboratory results.

Patients may discontinue therapy at any time. Patients will attend the EOT visit 30 (± 7) days after completion of their last dose of brentuximab vedotin.

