SAEs	SAEs will be collected from signing of the main ICF through 30 days after the last dose of brentuximab vedotin.						
CTs of the neck, abdomen, and pelvis ^g	X		X	X		X	
Skin evaluation ^h	X		X	X		X	
PET/CT ⁱ	X		X				
Survival and disease status							X ^j

- a. All treated patients will be followed for PFS and OS status every 12 weeks (\pm 1 week) until the study closure. For patients who have progressive disease, survival/disease status and information regarding the initiation of an alternative lymphoma treatment may be obtained by phone call.
- b. Tumor tissue at any time will be collected (five unstained slides at 4 μ m thickness or a paraffin-embedded block) after the patient has signed the screening ICF. This will be used to assess CD30 status using Ber-H2 antibody (DAKO, Glostrup, Denmark) and biomarkers associated with sensitivity or resistance to brentuximab vedotin (eg, beta3- tubulin etc). Biomarker samples will be collected (EDTA 5mL x1 plus SST 3mL x1) to assess lymphocyte subsets and soluble CD30 quantification.
- c. The Cycle 1 Day 1 physical exam is not required if the screening physical examination was conducted within 7 days before administration of the first dose of brentuximab vedotin. A limited physical exam may be administered at the treating physician's discretion.
- d. A serum β -hCG pregnancy test will be performed for women of childbearing potential during screening. A negative urine pregnancy test is required if the serum pregnancy test was not done within 7 days of the first dose of study drug.
- e. Vital signs should be measured at screening and within 1 hour prior to infusion of brentuximab at day 1 of each cycle and EOT.
- f. A blood sample for hematology and serum chemistry including LDH will be obtained at screening and pre-dose at day 1 of each cycle and EOT. Hematology and chemistry blood samples for cycle 1, day 1 may be collected within 7 days prior to dosing to ensure patient eligibility on study day 1.
- g. Response to treatment and disease status assessments will be evaluated according to the Revised Response Criteria for Malignant Lymphomas¹ and the modified SWAT criteria.² MRI scans may be substituted for CT scans only if a patient 1) has a glomerular filtration rate of less than 60 mL/min such that IV contrast presents a risk of renal failure, 2) develops anaphylaxis to IV contrast, or 3) becomes pregnant during long-term follow-up. If use of MRI is required, a consistent scanning modality must be maintained.

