
During the treatment phase CT scans will be performed at:

- 1) Screening
- 2) CT scans of involved sites after cycle 2 of brentuximab every 6 weeks (window, \pm 7 days) until progressive disease or 16th cycle of brentuximab vedotin. After last dose of cycle 16: between 4 and 8 weeks following last dose of brentuximab. During the follow-up period: every 3 months until the study closure.
- h. In case of cutaneous lymphomas, total body skin scoring is calculated based on modified Severity Weighted Assessment Tool (mSWAT). This involves the direct assessment of the BSA of each type of skin lesions (palm plus fingers of the patient = approximately 1% BSA) in each of 12 areas of the body, multiplying the sum of the BSA of each lesion by a weighting factor (patch=1, plaque =2, and tumor = 3 or 4) and generating a sum of the subtotals of each lesions.
- i. This is mandatory at sites where a PET scanner is available. For all patients, if the screening FDG-PET scan is non-avid, the second interim FDG-PET scan will not be performed.
- j. Subjects will be followed for survival disease status every 3 months till the study closure.

TABLE OF CONTENTS

STUDY OVERVIEW DIAGRAM	5
SCHEDULE OF EVENTS	6
LIST OF TABLES	9
1 BACKGROUND AND STUDY RATIONALE.....	16
1.1 Scientific Background	16
1.1.1 Disease Under Treatment.....	16
1.1.2 Study Drug	16
1.2 Preclinical Experience.....	17
1.3 Pharmacology and Drug Metabolism in Humans	17
Pharmacokinetic properties	17
1.4 Clinical Experience	18
1.5 Study Rationale and Selection of Study Drug Doses.....	21
1.6 Potential Risks of brentuximab vedotin	22
2 STUDY OBJECTIVES	25
2.1 Primary Objectives.....	25
2.2 Secondary Objectives.....	25
2.3 Exploratory Objectives.....	25
3 STUDY ENDPOINTS	26
3.1 Primary Endpoints.....	26
3.2 Secondary Endpoints.....	26
3.3 Exploratory Endpoints	26
4 STUDY DESIGN.....	27
4.1 Overview of Study Design.....	27
4.2 Number of Patients.....	27
4.3 Duration of Study.....	27
5 STUDY POPULATION	28
5.1 Inclusion Criteria.....	28
5.2 Exclusion Criteria.....	29
6 STUDY DRUG	30
6.1 Brentuximab Vedotin Administration.....	30
6.2 Dose Modification Guidelines	31
6.3 Excluded Concomitant Medications and Procedures.....	32
6.4 Permitted Concomitant Medications and Procedures	33
6.5 Precautions and Restrictions	33
6.6 Management of Clinical Events	34
6.7 Description of Investigational Agents.....	37
6.8 Preparation, Reconstitution and Dispensing	38
6.9 Packaging and Labeling	38
6.10 Storage, Handling and Accountability	38

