12.4 Modified SWAT criteria for skin lesions

Definitions of skin lesions

1. Patch: any size lesion without induration or significant elevation above the surrounding uninvolved skin: poikiloderma may be present.
2. Plaque: any size lesion that is elevated or indurated: crusting or poikiloderma may be present.
3. Tumor: any solid or nodular lesion ≥ 1 cm in diameter with evidence of deep infiltration in the skin and/or vertical growth.

Modified SWAT tool

Body Region	% BSA in Body Region	Assessment of Involvement in Patient's Skin		
		Patch*	Plaque†	Tumor‡
Head	7			
Neck	2			
Anterior trunk	13			
Arms	8			
Forearms	6			
Hands	5			
Posterior trunk	13			
Buttocks	5			
Thighs	19			
Legs	14			
Feet	7			
Groin	1			
Subtotal of lesion BSA				
Weighting factor		$\times 1$	$\times 2$	$\times 4$
Subtotal lesion BSA \times weighting factor				

NOTE. mSWAT score equals summation of each column line.

Abbreviations: BSA, body surface area; mSWAT, modified Severity Weighted Assessment Tool.

*Any size lesion without induration or significant elevation above the surrounding uninvolved skin; poikiloderma may be present.

†Any size lesion that is elevated or indurated; crusting, ulceration, or poikiloderma may be present.

‡Any solid or nodular lesion ≥ 1 cm in diameter with evidence of deep infiltration in the skin and/or vertical growth.

Response in skin

T1 Limited patches, papules, and/or plaques covering < 10% of the skin surface; may further stratify into T1a (patch only) v T1b (plaque ± patch)

T2 Patches, papules, or plaques covering ≥ 10% of the skin surface; may further stratify into T2a (patch only) v T2b (plaque ± patch)

T3 One or more tumors (≥ 1 cm diameter)

T4 Confluence of erythema covering ≥ 80% body surface area

Response	Definition
Complete response	100% clearance of skin lesions*
Partial response	50%-99% clearance of skin disease from baseline without new tumors (T ₃) in patients with T ₁ , T ₂ or T ₄ only skin disease
Stable disease	< 25% increase to < 50% clearance in skin disease from baseline without new tumors (T ₃) in patients with T ₁ , T ₂ , or T ₄ only skin disease
Progressive disease ^t	≥ 25% increase in skin disease from baseline or New tumors (T ₃) in patients with T ₁ , T ₂ or T ₄ only skin disease or Loss of response: in those with complete or partial response, increase of skin score of greater than the sum of nadir plus 50% baseline score
Relapse	Any disease recurrence in those with complete response

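### No mSWAT skin score is scheduled after the end-of-treatment visit, so score-based skin progression may be missed or dated late and DOR and PFS may be overstated in cutaneous patients

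*Combined protocol and SAP*

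**What the plan says.** Cutaneous disease is in scope. Section 5.1 lists hydroa vacciniforme-like T-cell lymphoma as eligible and accepts a lesion measurable by mSWAT, and section 4.1 assigns mSWAT to cutaneous cases for response.

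The schedule of skin and CT assessments is spread over four places:

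- **Section 4.1.** "Tumor measurements will be assessed (CT and PET scans) at screening, after completion of cycle 2", and again 4 to 8 weeks after the last dose. After that, "CT scans only will be used for the disease assessment follow-up every 3 months until the study closure".
- **Schedule of Events, row "Skin evaluation ^h".** Marked at screening, Cycle 2, Cycles 3~15 and EOT/EOS. The FU cell is blank.
- **Schedule of Events, row "CTs of the neck, abdomen, and pelvis ^g".** Same pattern, also blank at FU. Footnote g then supplies the follow-up scans: "During the follow-up period: every 3 months until the study closure".
- **Footnote h.** "In case of cutaneous lymphomas, total body skin scoring is calculated based on modified Severity Weighted Assessment Tool (mSWAT"). It goes on to explain how the score is built and gives no visit times.

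Appendix 12.4 defines skin progression as an increase of at least 25% from baseline, or new tumors in patients with T1, T2 or T4 disease only, or loss of response, meaning a score above nadir plus 50% of the baseline score. Relapse after a complete response is "Any disease recurrence in those with complete response". Section 7.1.6 ends DOR at progression. It gives no assessment schedule for DOR or PFS, and no censoring rule for either.

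**The concern.** Two of the skin progression criteria are thresholds on a number, the mSWAT score. CT does not measure the body surface area of patches or plaques. Once the EOT visit has passed, no text schedules the measurement that those criteria need, while nodal disease continues to be measured every 3 months.

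The patients affected are those with cutaneous lymphoma who stop treatment without progression, above all skin partial responders. If their skin progression is found late or not at all, their DOR and PFS times run on. They are pooled in the same Kaplan-Meier curves as patients whose disease is still being measured. Both endpoints are named secondary endpoints in section 3.2, and section 4.3 sets the study duration to reach the final analyses of ORR and PFS. With 25 patients, a few late dates can move the curves.

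**Working it through.** **Plan's own figures.** The plan states no number for DOR or PFS. Its only design figure is the Simon rule in section 7.1.1: 2/10, then 7/22, with p0 = 0.20 and p1 = 0.45. An exact two-stage binomial calculation gives alpha 0.0492 and power 0.8065, and a search confirms that this is the optimal design. Both 22/0.9 and 22 × 1.1 round up to 25. Response is judged during treatment and at EOT, where skin scoring is marked, so a follow-up skin score changes none of this.

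**Which skin events need a score after EOT**

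| Event (Appendix 12.4) | Needs mSWAT score? | Scheduled in follow-up? |
|---|---|---|
| Recurrence after skin CR | No | Physical exam |
| New tumors (T1, T2 or T4 only) | No | Physical exam |
| Increase of at least 25% from baseline | Yes | No score scheduled |
| Loss of response beyond nadir + 50% of baseline | Yes | No score scheduled |

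**Time at risk after EOT.** Cycles last 21 days and EOT is 30 days after the last dose.

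- 16 cycles: (15 × 21 + 30)/30.4375 = 11.3 months after first dose. With closure at month 30, at most 18.7 months remain. Under uniform accrual over 24 months, 18.7/24, about 78%, of such patients have some post-EOT follow-up.
- 9 cycles: (8 × 21 + 30)/30.4375 = 6.5 months, and about 98% have some.

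**Share of relapses falling after EOT.** Assume response at week 6 and exponential DOR. The share is 2^(−t/m), where t is weeks from response to EOT and m is the median DOR. The medians are borrowed from the protocol: 36 weeks (DLBCL, section 1.5) and 6.7 months, about 29.1 weeks (Hodgkin lymphoma, section 1.4).

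- 6 cycles: the sixth dose is at week 15, so EOT is at 15 + 30/7 = 19.3 weeks and t = 13.3. Shares are 2^(−13.3/36) = 77% and 2^(−13.3/29.1) = 73%.
- 16 cycles: EOT is at 45 + 30/7 = 49.3 weeks and t = 43.3. Shares are 43% and 36%.

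These are shares of relapses occurring after the last scheduled skin score. They are not shares missed, and they ignore study closure.

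**Effect on pooled median DOR.** Assume a cutaneous share f of responders (10%, 20%, 40%), response at 1.4 months, and the worst case: every post-EOT skin relapse is missed and the patient is carried as progression-free to closure. Let q be the time from response to EOT and S = 2^(−q/m). If m is at most q, the median does not move. Otherwise the observed median solves f·S + (1 − f)·2^(−t/m) = 0.5. For 9 cycles, q = 6.5 − 1.4 = 5.1 months.

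| True median (months) | f = 10% | f = 20% | f = 40% |
|---|---|---|---|
| 5.0 (21.7 weeks, section 1.5) | 5.0 | 5.0 | 5.0 |
| 6.7 | 6.9 | 7.1 | 7.9 |
| 8.3 (36 weeks) | 8.7 | 9.2 | 11.0 |

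A simulation of 200,000 patients agrees (8.0 and 11.1 in the last column), so the largest shift is about 2.8 months. With EOT after 16 cycles, q = 9.9 months exceeds every assumed median and no median moves. If cutaneous patients are instead censored at their last mSWAT, the simulated medians do not change materially.

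The range of 0 to about 2.8 months covers EOT after 9 or 16 cycles and is not an upper bound. With EOT after 6 cycles, q = 4.4 − 1.4 = 3.0 months. At m = 8.3 and f = 40%, S = 0.776 and the formula gives about 13.8 months.

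**The case against.** The case against a stronger reading is good, and most of it stands.

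- **CT scans only.** The sentence before it speaks of CT and PET, so the phrase most naturally means CT without PET. That paragraph of section 4.1 does not mention skin scoring at screening or after cycle 2 either, where the schedule plainly requires it. It should not be read as forbidding skin assessment in follow-up.
- **The blank cell.** The CT row is blank at FU too, so the blank alone proves little. The evidence is the contrast between the footnotes: g adds follow-up times and h does not.
- **Other text.** Footnote g says "Response to treatment and disease status assessments will be evaluated according to the Revised Response Criteria for Malignant Lymphomas¹ and the modified SWAT criteria", without limiting this to the treatment phase. Footnote a follows all treated patients for PFS every 12 weeks, and the physical exam and disease-status rows are marked at FU. A site may therefore score the skin, but nothing requires it. Naming a criterion does not schedule its measurement.
- **Other PFS events.** Death counts, and so does new anticancer therapy in confirmed non-complete responders. This is a partial backstop for skin partial responders, but it dates the event at the new therapy and not at progression. DOR as defined ends only at progression.

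A reader might infer that skin relapse cannot be scored after EOT, or that DOR and PFS are certain to be overstated. The documents support neither. mSWAT is a bedside estimate that can be done at any visit, two of the skin events need no score, and the bias depends on how patients are censored.

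**Conclusion.** The gap is real and limited. No mSWAT assessment is scheduled after EOT, although two of the plan's own skin progression criteria need one. In cutaneous patients who stop treatment without progression, score-based progression may be missed, dated late or recorded differently between sites, so DOR and PFS in these patients may be overstated.

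The size cannot be fixed from the documents. It rests on the number of cutaneous responders, when they stop, how much the FU exam detects, and the missing censoring rule. The illustrated shifts further assume exponential DOR, medians borrowed from other lymphomas and, where the median moves, complete non-detection. The point concerns secondary endpoints in a subgroup of unknown size. The primary analysis is untouched. It is still worth correcting before follow-up data accrue, because a skin score that was not taken cannot be recovered later.

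**What to change.** 1. Mark Skin evaluation in the FU column for patients with skin disease at baseline, every 3 months alongside the CT until progression.
2. Add to footnote h the follow-up timing that footnote g gives for CT.
3. Reword section 4.1 so that three-monthly follow-up uses CT and, for cutaneous lymphoma, mSWAT as well. If the present wording is meant only to drop PET, say so.
4. In section 7.1.6, state that DOR and PFS in these patients use both CT and mSWAT, and that patients without an event are censored at the last adequate assessment by both.

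The cost is one schedule mark, a few sentences and a few minutes of scoring at a visit that already includes a physical exam. No new visit or equipment is needed, and the sample size does not change.
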